of the first Veteran-peer encounters will involve accompanying the Veteran to his first VHA health care appointment and orienting him to check-in, appointment making, laboratory, and pharmacy. Other encounters may include reviewing health-related priorities and goal setting, assistance with health tasks (e.g. refilling prescriptions), and brief motivational interviewing related to health goals. Training of peers will be conducted by Drs. [name], [name], [name] and [name], over a 4-day period, at Bedford VAMC. Following training, the HCRV team (VISN coordinator(s), outreach specialists, and peers) will participate on twice monthly conference calls, led by the trainers and the external facilitators ([name] and [name]), to discuss issues that arise in the use of peer support.

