Phase 1: Contextual Analysis and Preparation for Implementation in Massachusetts. We will conduct contextual analysis (Chambers, Mustard et al. 2013; Chambers, Glasgow et al. 2013; Lyon, Pullmann et al. 2015) through interviews and network mapping (Aim 1). At the end of this phase the findings will be incorporated into the peer-support guidebook. This phase will involve interviewing Veterans (thrice over 6 months) and stakeholders (once). Network mapping is a technique used in business and engineering, and is increasingly being applied in health care. It involves documenting potential paths that individuals and groups follow in the process of accomplishing a task (here, linkage to primary care and other health services)(Lyalin and Williams 2005; Williams, Lyalin et al. 2005; Rico, Yalcin et al. 2014). We use interview questions that seek temporal, spatial, and participatory information. The timing, sequence, and duration of Veterans' contacts with individuals and organizations are mapped in an activity diagram (Lyalin and Williams 2005), which are then combined to comprehensively map the network of reentry-related contacts that Veterans make. These maps may reveal unhelpful contacts, waiting between contacts, and useful but infrequently tapped resources. Population: There are about 200 Veterans, released from Massachusetts prisons each year. Recruitment of Veterans: We will use a method currently in use VHA by a contractor, Policy Research Associates (Delmar, NY), to contact reentry Veterans. During prison visits, the outreach specialists will collect contact information from incarcerated Veterans who indicate willingness to participate in the project after their release. The outreach specialist will provide our team with the contact sheets of those Veterans and their release dates. We will contact these Veterans after their release, enrolling 10 Veterans. Inclusion/Exclusion: Released from an MA state prison, eligible for VHA services, and no history of dementia.

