Phase 2 - MA Implementation of Peer Support. This phase involves implementation and evaluation of the peer-support intervention in MA. For Population, Recruitment of Veterans, Inclusion/Exclusion, see Phase 1, above. Our target is 30 Veterans receiving peer support. We will enroll Veterans on a rolling basis as released from MA correctional facilities. We will use HOMES database to create a matched comparison group of Veterans released in the same time period in MA, matching on demographics, SUD/MH diagnoses, criminal offense, length of incarceration, and # of arrests. Intervention will last for 6 months for any single Veteran, with peers having caseloads of 15 Veterans (Dihoff 2009). A VISN 1 outreach specialist, [name], will serve as

internal facilitator, while [name] and [name] will be external facilitators. Peer Training: see above in “Peer-Support Intervention”.

Data Sources, Collection and Analysis: Peers will administer a health care utilization questionnaire with intervention Veterans at baseline (week 1) and at 6 months to capture information about VA and non-VA health service use (the former for comparison with VA medical record data).

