Analysis Plan

Official Title: Veterans Justice Reentry (Post-Incarceration) (QUE 15-284)

Brief Title: Improving Linkage to Health and Other Services for Veterans Leaving Incarceration (PIE)

ClinicalTrials.gov ID: NCT02964897

Unique Protocol ID: QUX 16-012

Study Principal Investigator: D. [name] MS BA

Document date: September 7, 2021

Analysis Plan:

Improving Linkage to Health and Other Services for Veterans Leaving Incarceration (ID QUX 16-012)

We will enroll Veterans on a rolling basis as released from MA correctional facilities. We will use HOMES database to create a historical comparison group comprised of all Veterans released in MA in the two-year period directly preceding the start of the PIE intervention and who accessed VA Health Care for Reentry Veterans (HCRV) services.

Quantitatively, we will use HOMES and CDW to compare intervention and comparison Veterans with respect to their baseline demographic characteristics (age, gender, race, ethnicity, marital status, self-rated health) and our outcomes interest. Also for intervention Veterans we will have self-report diagnoses and utilization from baseline and 6-month follow up (including utilization of non-VA health care sources). We will compare rates of visits for primary care, outpatient MH treatment, outpatient SUD treatment, as well as missed opportunities (e.g. no shows) between intervention and comparison groups using t-tests and chi-square tests. For our secondary measures we will also compare intervention to comparison on ER and hospital use (episodes and # of days) during the 6-month reentry period.

Analysis involves two phases. First, we use descriptive statistics to summarize the volume and intensity of peer activities in support of the Post-Incarceration Engagement (PIE) intervention participants. Secondly, to examine access to and engagement in care outcomes, we compare our measures of linkages to VA health care following release between PIE participants and our historical comparison group. Specifically, we use bivariate tests (Chi-Square/Fisher Exact Tests and t-tests, as appropriate) to assess the relationship between participation in the PIE intervention and linkages with VA health care.

Summary of key variables

- Demographics (age, gender, race, ethnicity, marital status, self-rated health)
- SUD diagnoses
- MH diagnoses
- Criminal offense
- Length of incarceration
- # of arrests
- Housing/homeless experience
- Major comorbidities (out of list of 10-12)

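### PIE enrolment follows release with no stated maximum interval while linkage is counted from release, so visits before first peer contact can count as PIE linkage; a landmark analysis should be added

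*SAP*

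**What the plan says.** In its second analysis phase the SAP states: "we compare our measures of linkages to VA health care following release between PIE participants and our historical comparison group". The comparators are Veterans released in Massachusetts in the two years before PIE began who used HCRV services. The SAP gives no start or end date for the linkage count. Its only stated window is the 6-month reentry period, given for the secondary measures.

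Entry to PIE is described in Protocol section 3. Phase 2 says "For Population, Recruitment of Veterans, Inclusion/Exclusion, see Phase 1, above", and the Phase 1 text reads "We will contact these Veterans after their release, enrolling 10 Veterans". The criteria are "Released from an MA state prison, eligible for VHA services, and no history of dementia". They set no upper limit on time since release and do not ask about earlier VHA visits. Exposure is fixed per person: "Intervention will last for 6 months for any single Veteran".

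Other text points to early entry:

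- The SAP, like Phase 2 of the Protocol, says "We will enroll Veterans on a rolling basis as released from MA correctional facilities".
- The Phase 2 utilization questionnaire is given "at baseline (week 1) and at 6 months".
- Phase 1 interviews begin 1 week after release.
- Outreach specialists pass on contact sheets and release dates.
- One of the peer's early tasks is "accompanying the Veteran to his first VHA health care appointment".

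**The concern.** In a non-randomised comparison, eligibility, start of exposure and start of follow-up should coincide, or be given the same offset in both groups. Here follow-up starts at release for everyone, but a PIE Veteran joins the group only once the team has reached and enrolled him. A comparator need not be reachable on any particular day after release.

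Two things follow. A VHA visit between release and first peer contact can be counted as linkage in the PIE group. And a Veteran who drops out of reach soon after release never becomes a PIE participant, while his historical counterpart stays in the comparison denominator.

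The planned chi-square, Fisher and t-tests cannot adjust for either. The stake is less a significance claim, which the Protocol disowns, than the effect size: Additional Design Considerations says these results will be used to size the next study.

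**Working it through.** **Input from the plan.** Specific Aims reports that 43% of eligible HCRV Veterans have no VHA outpatient contact in the first 4 months. 100 − 43 = 57%, which reproduces the rate used in Additional Design Considerations. The planned PIE group is 30. The plan gives no figure for the entry delay or for this bias.

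**Assumptions.** Usual-care linkage has a constant hazard h until peer contact; entry is at delay d; already-linked Veterans are r times as likely to be enrolled as others; the window is 6 months from release.

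**Step 1: hazard.** h = −ln(0.43)/4 = 0.211 per month. Usual-care linkage at 6 months = 1 − exp(−0.211 × 6) = 71.8%.

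**Step 2: share already linked at entry.** a = 1 − exp(−h·d).

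| Entry | a | Of 30 |
|---|---|---|
| 1 week | 4.7% | 1.4 |
| 2 weeks | 9.2% | 2.8 |
| 4 weeks | 17.6% | 5.3 |
| 1 month | 19.0% | 5.7 |
| 8 weeks | 32.2% | 9.7 |

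Linear accrual to 57% gives less: 1.0, 2.0, 3.9 and 7.9 of 30 at 1, 2, 4 and 8 weeks.

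**Step 3: false gain with no peer effect.** The already-linked share among those enrolled is f = a·r/(a·r + 1 − a). PIE linkage = f + (1 − f)(1 − exp(−h(6 − d))). For d = 1 week (0.23 month) and r = 3: f = 0.142/(0.142 + 0.953) = 0.130, and PIE linkage = 0.130 + 0.870 × 0.704 = 74.2%. Gains below are against 71.8%, from unrounded values.

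| r | Entry 1 week | Gain | Entry 1 month | Gain |
|---|---|---|---|---|
| 1 | 71.8% | 0.0 | 71.8% | 0.0 |
| 1.5 | 72.5% | 0.7 | 74.3% | 2.4 |
| 2 | 73.1% | 1.3 | 76.3% | 4.5 |
| 3 | 74.2% | 2.4 | 79.6% | 7.8 |

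The r = 1 row matters most: without selective enrolment, the shared release clock gives no false gain at any delay.

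**Step 4: reachability.** Suppose a share q of releasees drops out of reach before entry and never links. PIE linkage with no effect is then 57%/(1 − q): 60.0% at q = 5%, 63.3% at 10% and 71.2% at 20%. The documents give no value for q.

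**Step 5: dilution.** Suppose peers double the hazard after entry. In weeks, h = 0.0485 and 4 months = 17.4 weeks. The 4-month difference counted from release is 1 − exp(−h·d − 2h(17.4 − d)) − 0.57: 23.6 points for entry at week 1, 20.5 at week 4 and 15.7 at week 8. Among those unlinked at entry, followed to 4 months in both groups, the differences are 24.8, 25.0 and 23.2 points. The landmark contrast is much less sensitive to delay.

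**The case against.** The strongest reply has three parts.

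First, the plan means to enrol people almost at release. The Phase 1 procedure that Phase 2 adopts was written to reach Veterans for a 1-week interview, and the Phase 2 baseline is also at week 1. This stands as evidence of intent. It is not an eligibility limit or an analysis rule, and Phase 2 does not say whether week 1 runs from release or from the start of peer support. A reader might infer that Veterans could routinely join many weeks after release; the documents do not support that.

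Second, counting from release is symmetric, because early usual-care visits count for comparators too. This stands. A reader might infer that crediting PIE with visits before peer contact must inflate its result. The r = 1 row shows that it does not, and step 5 shows that late entry alone pulls the difference down. Upward bias needs selective reach or enrolment, which the documents neither show nor exclude.

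Third, linkage from release is a sensible target for a reentry programme, and the project is not designed to show a significant effect. That is a good reason to keep the release-anchored comparison, but not to leave its window undefined or the entry delay unreported.

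**Conclusion.** The point holds in a limited form. Entry follows release with no stated maximum, linkage is counted from release, and nothing separates visits before first peer contact from those after it or gives comparators a matching start. The net direction of bias is unknown: late entry dilutes, selective reach or enrolment inflates.

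If entry is at about 1 week, as the schedule suggests, the effect is small: 1 to 2 of 30 already linked, and a false gain of about 0.7 to 2.4 points under assumed enrolment ratios of 1.5 to 3. At 1 month the figures are 19% and about 2 to 8 points. All rest on a constant hazard and on delays and ratios that the documents do not give.

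A reader might also infer a bias from early re-incarceration. The structure allows it, but no rate is given and neither document says that HOMES or CDW records it, so its size cannot be stated. Severity is minor to moderate.

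**What to change.** In the SAP:

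1. Keep the release-anchored comparison and state its window.
2. Add a landmark analysis. Start PIE follow-up at enrolment or first peer contact (name which). Start each comparator at a number of days after release drawn from the PIE delay distribution. Follow both groups for the same period.
3. For first linkage in the landmark analysis, exclude from both groups anyone with a qualifying VHA visit between release and the start day. Visit counts can keep everyone.
4. Tabulate days from release to first peer contact, and PIE visits before and after it.
5. Restrict comparators to those in the community on the start day only if the data show it; otherwise state this as a limitation.

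**Cost.** A little programming. Release dates, CDW visits and the peers' encounter forms are already part of the project. Already-linked PIE Veterans leave the landmark first-linkage analysis: without selective enrolment about 1 to 6 of 30 for entry at 1 to 4 weeks. With ratios of 1.5 to 3 the loss is larger: 30f is about 4 to 7 at 2 weeks and 8 to 12 at 1 month. With 30 participants that loss of precision is real, which is another reason to report the landmark result beside the release-anchored one and not in its place.

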1. SPECIFIC AIMS

Veterans leaving incarceration (henceforth, “reentry Veterans”) are among the most underserved by the VA and thus are an increasingly high priority population. The Bureau of Justice Statistics estimates that 140,000 Veterans are incarcerated in the U.S. at a given time, approximately 80% of whom are eligible for VA benefits (Noonan 2007). Among Veterans incarcerated in state prisons nationally, 75% reported using drugs prior to incarceration, and roughly 25% of those reported injection drug use history (Noonan 2007). Also, about 50% of incarcerated Veterans report having recently experienced symptoms of mental health disorders (Noonan 2007). Veterans are more likely to report a recent history of mental health (MH) service use (30%) than non-Veterans (24%) (Noonan 2007). The VA’s national Health Care for Reentry Veterans (HCRV) program identifies 10,000-15,000 incarcerated Veterans annually preparing to transition back to the community (2014). Despite many health needs, it is difficult to link reentry Veterans to Veterans Health Administration (VHA) primary care (the gateway to all VHA health care services). Lack of linkage to health care can lead to a downward spiral in health and mental health from worsening substance use disorders (SUDs) or MH, or from complications from hypertension and diabetes. This worsening health can lead to inefficient use of emergency and hospital services, and can derail progress in vocational training, education, work, and housing, which may lead to re-offending and re-incarceration ([name] 2003; Travis 2005; Mallik-Kane 2008; Baillargeon, Giordano et al. 2009; Meyer, Chen et al. 2011; [name] 2015).

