Implementation Frameworks and Strategy: Guided by our QUERI's selection of Consolidated Framework for Implementation Research (CFIR), we will ensure that our intervention is appropriate for the contexts in different states. Context, in CFIR, is delineated by the domains of Outer Setting (e.g. external policies, patient needs and resources) and Inner Setting (e.g. structure of the organization, culture). As with the other BridgeQUERI projects, we have selected facilitation as our implementation strategy. In addition our peer-support intervention is enhanced by the Behavioral Model for Vulnerable Populations (BMVP), (see description of BridgeQUERI Implementation Core), namely **Predisposing** characteristics (demographics, social structure, health beliefs), **Enabling** characteristics (personal/family, community, insurance, competing needs, ability to negotiate bureaucracy), and health-related **Need** based factors(perceived and evaluated health conditions). We propose both **external** and **internal** facilitation, because we are working in a complex setting with a highly complex population (Stetler, Legro et al. 2006; Jones, Auton et al. 2008; Kirchner, Kearney et al. 2014). To our knowledge there has been no evaluation of facilitation as an implementation strategy for state-level implementation of a VA program. Thus we have an excellent opportunity to contribute to the VA knowledge base on using facilitation as an implementation strategy. Additionally, we will vary the organizational level of internal facilitation. The internal facilitator will be one of the Outreach Specialists ([name], LCSW). Facilitation will include use of a manualized peer-support training (using a peer-support guidebook from Aim 1), and ongoing problem solving and technical assistance provided to VISN HCRV leadership, outreach specialists, and peers over the course of the project. Our implementation strategy was developed with our operational partners at HCRV program. They have great interest in HCRV program differences from state to state, realizing that states vary considerably in the resources available for reentry programs, and the supportiveness of the culture in relation to ex-offenders.

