Project Plan Overview: We propose to implement the Post Incarceration Engagement intervention in Massachusetts using a facilitation implementation strategy. We conduct formative and summative analyses, including assessment of fidelity, and a matched comparison group to evaluate the intervention's Veteran outcomes of linkage and engagement in VHA health care (using health care utilization measures). The project proceeds in 3 phases (see Figure 1). First, in preparation for implementation of peer-support intervention in the first state, we will conduct a contextual analysis in MA of the resources available in VHA and in community organizations to meet the needs of Veterans released from incarceration (Aim 1), development of peer-support guidebook (based on findings of the contextual analysis) and hiring of 2 peers. Next the intervention will be implemented in MA (Aim 2). It will last 6 months with a total of 30 Veterans receiving the peer support. We will identify a matched sample of comparison reentry Veterans. Qualitative formative and summative interviews will be conducted with a sample of stakeholders and Veterans to assess fidelity of the intervention. A review of peer worksheets documenting contacts with Veterans will also help evaluate fidelity evaluation. Utilization of VHA primary care, mental health care, and SUD care will be evaluated through chart reviews, and self-report (self-report for intervention Veterans only). Finally we will develop a proposal for the spread of this intervention through the use of a cluster-randomized multi-VISN hybrid implementation-effectiveness study (Aim 3).

Design and Methods: Key Outcomes: Our Veteran level outcomes include # of primary care visits, MH visits, and SUD visits (where diagnosis indicates appropriateness); and missed opportunity rates (no-shows and cancellations) for primary care, MH, and SUD visits. Secondary outcomes include # of emergency room (ER) visits, hospitalizations, and hospital days – these are also being assessed in the BridgeQUERI MISSION project, providing cross-project comparisons. Our main implementation outcome will be fidelity of the intervention as implemented, in comparison to core elements as contained in the peer-support guidebook. We use a practical approach based on the NIH's Behavioral Change Consortium fidelity framework for psychosocial Treatments (Bellg, Borrelli et al. 2004). Our two primary fidelity measures are number of peer

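### The SAP swaps the protocol's matched same-period comparators for an unmatched historical group and compares linkage without correcting for measured imbalance

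*SAP*

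**What the plan says.** **Protocol.** Section 3 (Procedures), Project Plan Overview, states: "We will identify a matched sample of comparison reentry Veterans". Phase 2 of the same section calls this a "matched comparison group of Veterans released in the same time period in MA, matching on demographics, SUD/MH diagnoses, criminal offense, length of incarceration", and adds number of arrests to the matching factors. The Phase 2 Analysis paragraph then names only t-tests and chi-square tests. The Key Covariates paragraph plans a check for substantial baseline differences using CDW and HOMES. It names prior VHA use, and time since that use, among the factors that might partly explain differences in outcome.

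**SAP.** The Analysis Plan uses a historical group "comprised of all Veterans released in MA in the two-year period directly preceding the start of the PIE intervention", restricted to Veterans who accessed HCRV. It states no matching, weighting, stratification or regression, and gives no reason for the change. Groups are compared at baseline "with respect to their baseline demographic characteristics (age, gender, race, ethnicity, marital status, self-rated health"), and on outcomes. For linkage, "we use bivariate tests (Chi-Square/Fisher Exact Tests and t-tests, as appropriate) to assess the relationship between participation in the PIE intervention and linkages" with VA care. The protocol's matching factors appear under Summary of key variables but have no role in the linkage comparison. Prior VHA use does not appear in the SAP.

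**The concern.** Matching was the protocol's one concrete control for confounding, since its tests were also unadjusted. The SAP drops matching and puts nothing in its place, although the data for a correction are largely in HOMES and CDW.

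The stake is the effect estimate, not a significance claim. The protocol's Additional Design Considerations say the project is not designed to show a significant effect. The same paragraph relies on the measured outcomes for effect sizes and sample sizes in the next study, and Section 4 (Impact) expects the project to help answer whether peer support raises linkage. Measured imbalance could move that estimate either way, and its confidence interval would give no sign of it.

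**Working it through.** **The plan's own figure.** Additional Design Considerations say that 30 versus 30 gives 80% power at the 0.05 level for a 20% rise from 57%. Read as percentage points (57% vs 77%), the pooled two-sided formula gives 37.5% power, and 80% power needs 86 per arm. That mismatch is a separate matter. The 86 serves only as a reference below.

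**Inputs from the documents.** 30 PIE Veterans. Linkage of 57%, which is an HCRV rate for outpatient contact within 4 months (Section 1). About 200 releases a year in Massachusetts (Phase 1), so at most 2 × 200 = 400 historical comparators before the HCRV restriction.

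**Assumed inputs.** A low value of 100 comparators, and all covariate prevalences and effects below. The documents give no covariate distributions.

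**Step 1: sampling error under no effect.** SE = √[0.57 × 0.43 × (1/30 + 1/m)], which is 10.3, 9.7 and 9.4 points for m = 100, 200 and 400.

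**Step 2: a factor the protocol would have matched on (MH diagnosis).** Assume 50% prevalence among comparators. Section 1 says, nationally, that "about 50% of incarcerated Veterans report having recently experienced symptoms of mental health disorders". Bias = (linkage difference by diagnosis) × (difference in prevalence). With 10 to 30 points and ±10 to ±20 points, bias runs from ±0.10 × 0.10 = ±1 point to ±0.30 × 0.20 = ±6 points. Exact rejection rates of the two-sided chi-square test at 0.05, with no true effect:

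| Bias (points) | 30 vs 100 | 30 vs 200 | 30 vs 400 |
|---|---|---|---|
| −6 | 8.9% | 9.5% | 10.1% |
| −4 | 6.7% | 7.0% | 7.3% |
| −2 | 5.4% | 5.5% | 5.6% |
| 0 | 5.0% | 4.9% | 5.0% |
| +2 | 5.3% | 5.2% | 5.3% |
| +4 | 6.5% | 6.5% | 6.7% |
| +6 | 8.7% | 8.9% | 9.1% |

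**Step 3: prior VHA use.** This was never a matching factor, so the gap is shared by both documents. Assume 75% linkage in prior users and 40% in others. A 57% overall rate then implies a prior-user share of (0.57 − 0.40)/0.35 = 0.486 among comparators. If the PIE share x is 0.300 or 0.671, bias = 0.75x + 0.40(1 − x) − 0.57 = −6.5 or +6.5 points. The false-positive rate is 9.3% to 11.0%, and coverage of the Newcombe 95% interval is 89.0% to 90.6%.

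**Step 4: effect on planning.** Assume a true gain of 20 points, and take n per arm for 80% power from the estimated gain:

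| Bias (points) | −6.5 | −4 | 0 | +4 | +6.5 |
|---|---|---|---|---|---|
| n per arm | 198 | 139 | 86 | 58 | 46 |

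Sampling error has the larger effect. At 77% vs 57% the SE is 9.1, 8.4 and 8.1 points for 100, 200 and 400 comparators. An estimate one SE too low gives 312, 274 and 257 per arm; one SE too high gives 37, 39 and 40. These are individual-level figures and would not size a cluster-randomized study.

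**Step 5: would adjustment help?** Simulation with 6,000 runs per cell, 30 vs 100 and 30 vs 400, and four binary covariates with linkage effects of +35, +20, −10 and +5 points. Comparators were weighted to the PIE group by an estimated propensity score. Measured bias of ±4 to ±7 points fell to within 0.3 points. Root mean squared error was 8.3-10.0 points adjusted against 10.1-12.7 unadjusted, and adjusted interval coverage was 96-97%. Further runs with 100 comparators gave 12.4 to 9.3 points with strong covariates, 10.7 to 10.3 with moderate ones, and 10.4 either way with weak ones.

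**The case against.** **The historical group may be the better comparator.** Facilitation includes "ongoing problem solving and technical assistance provided to VISN HCRV leadership, outreach specialists, and peers", and those outreach specialists may also serve same-period comparators, so a pre-PIE group may avoid spillover. The HCRV restriction gives partial comparability. The group is also larger: the 30 vs 30 design has SE √[0.57 × 0.43 × 2/30] = 12.8 points. Adding a 6-point bias to the SAP design gives √(10.3² + 6²) = 11.9 points with 100 comparators and √(9.4² + 6²) = 11.1 with 400, both below 12.8. Matching on predictive factors would reduce the 12.8 somewhat, but matching on five domains from about 200 releases a year might not have balanced them fully. This stands: the change of comparator is not shown to be a net loss. It does not justify leaving measured imbalance uncorrected.

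**Part of the gap is not new.** Prior VHA use was never matched on, and the protocol's tests were unadjusted. The PIE group was always made up of volunteers, because specialists "collect contact information from incarcerated Veterans who indicate willingness to participate in the project after their release". The protocol's baseline check also covers prior VHA use, and the SAP does not withdraw it. All true, but that check describes imbalance and does not remove it.

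**The gain may be small, or adjustment may mislead.** With weak covariates, adjustment changes almost nothing, so it also costs almost nothing. It cannot remove unmeasured bias: with an added unmeasured 5-point difference, about 5 points remain and coverage is 90-94%. If measured bias is −6.5 points and the unmeasured bias opposes it, the unadjusted estimate is closer (about −1.5 against +5 points). That is a reason to report both estimates and to label the result non-causal.

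**Conclusion.** The concern holds and should be fixed; it is not fatal to an implementation pilot. The two documents define different comparators without explanation, and the SAP leaves the protocol's matching factors unused in the linkage comparison. The part specific to the SAP is an illustrative bias of ±1 to ±6 points. The ±6.5-point illustration for prior VHA use is a weakness of both documents. Both rest on assumed prevalences and effects, on 57% linkage and on 100 to 400 comparators; the true size and direction are unknown. The illustrated bias is smaller than one standard error, but unlike sampling error it is not reflected in the reported interval.

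**What to change.** 1. Reconcile the two comparator definitions and state why the historical group is used.
2. Keep the bivariate tests. Prespecify one adjusted comparison that weights or matches comparators to the PIE group on a few HOMES/CDW covariates: prior VHA use (to be added to the SAP's list), SUD/MH diagnosis, length of incarceration and age. With 30 PIE Veterans the list must stay short.
3. Report the adjusted difference in linkage with a 95% CI beside the unadjusted one, with standardized differences before and after. Use the adjusted difference, with its CI, as the planning estimate.
4. State that volunteering and calendar time remain uncontrolled and that the estimate is non-causal.

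**Cost.** SAP wording and modest programming on data largely already in HOMES/CDW. In the four-covariate simulation the effective comparator sample is 75-79% of nominal under imbalance (85-88% without). The 95% CI half-width is 17-21 points adjusted against 17-20 unadjusted.
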